6.2.1.2 Secondary Analyses

Treatment effect will be assessed within subgroups based on the following factors: age, gender, ethnicity, prior spectacle wear, phoria, baseline refractive error, and accommodative lag.

Compliance with spectacle wear will be compared between treatment groups using a qualitative estimate of how often during waking hours the spectacles are worn.

747 Point estimates of change in myopia will be obtained for each treatment group from baseline
748 to 1, 2 and 3 years and 95% confidence intervals calculated. Estimates of change between
749 successive visits and 95% confidence intervals also will be calculated.

750
751 Point estimates and 95% confidence intervals for change in accommodative response will be
752 calculated at 1 year, 2 years, and 3 years for each treatment group and change in
753 accommodative response will be compared between treatment groups using t-tests.

754

755 **6.2.1.3 Interim Analyses**

756 Given the expected duration of recruitment (approximately 16 months), it is not possible that
757 significant differences in SER at the primary outcome time (3 years) will be observed prior to the
758 end of recruitment. Based on the effect size for children meeting COMET2 criteria seen in
759 COMET, it also is unlikely that significant differences in the 3 year outcome will be observed
760 prior to most or all children reaching the 3 year follow-up visit. Although interim significant
761 differences at earlier follow-up times are possible, these may not be sustained through longer
762 follow-up and would not constitute a reason to stop recruitment or follow-up in the study.
763 Hence, a formal statistical monitoring plan for the primary outcome is not planned. However, an
764 efficacy and safety report will be provided to the DSMC twice each year.

765

766 **6.2.2 MEM and Nott Accommodation Ancillary Study**

767 Data analysis will consist of determining the sensitivity and specificity for MEM and Nott testing
768 methods. The Grand Seiko measurements of accommodative response will be considered the
769 gold standard. Sensitivity and specificity will be based on the ability of MEM and Nott testing
770 to properly classify patients as to whether reduced accommodative response is present.

771

772 95% confidence intervals will be calculated for both sensitivity and specificity for each testing
773 method.

774
775
776
~~777~~
779
780
781
782
783
784
785
786
787
788
789
790
791
792
793
794
795
796
797
798

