65 Rationale for Change

66 Because at enrollment spectacles are being prescribed according to the endpoint of the subjective
67 refraction and because it would be usual practice in spectacle changes to prescribe the endpoint
68 of the subjective refraction, it was felt that the protocol should require all spectacle changes be
69 prescribed as such.

70 **CORRECTION OF MYOPIA EVALUATION TRIAL 2 (COMET2)**

71 **A Randomized Trial of the Effect of Progressive Addition Lenses Versus Single Vision**
72 **Lenses on Low Myopia Associated with Large Accommodative Lags and Near Esophoria**
73 **in Children**

74 **PROTOCOL AMENDMENT #2 (3-9-06)**
75
76

77 This amendment provides for a protocol change to the randomized trial eligibility criterion for
78 accommodative response. The criterion for accommodative response will be lowered by 0.50 D,
79 therefore requiring a higher amount of accommodative lag for randomized trial eligibility.
80

81 Current Protocol

82 The current protocol specifies that patients are eligible for the randomized trial if their accommodative
83 response at 33 cm (3.0 D) is less than 2.50 D (i.e., lag of accommodation 0.50 D or greater) as
84 measured by non-cycloplegic autorefractometry with a Grand Seiko open field of view autorefractor.
85

86 Proposed Change

87 The proposal is to narrow the randomized trial eligibility criterion for accommodative response
88 to less than 2.00 D (lag of accommodation 1.0 D or greater) therefore requiring a higher amount
89 of accommodative lag for randomized trial eligibility.
90

91 Rationale for Change

92 We now have reason to believe that the accommodative response measured by the method used
93 in the current study is less than the accommodative response measured by the method used in
94 COMET, the study on which the rationale for COMET2 is based. The major difference between
95 the two methods of measuring accommodative response is the autorefractor. A Canon R-1 was
96 used in the COMET study whereas the COMET2 uses a Grand Seiko, a newer autorefractor
97 which is more accurate than the Canon R-1. Another difference is that in COMET, an eye was
98 tested while a Maddox rod and Risley prism were held in front of the other eye (allowing for
99 simultaneous measurement of phoria), whereas in COMET2 an eye is tested while an occluder is
100 held in front of the other eye. Results from a pilot study of 40 myopic young adults found that

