101 the accommodative response measured by the COMET2 method was 0.35 D less than by the
102 COMET method, meaning that the accommodative lag was greater by the same amount.

103 Therefore, COMET2 is very likely enrolling some patients with larger accommodative response
104 (i.e. less accommodative lag) than that of COMET patients in the subgroup which showed a
105 clinically meaningful treatment effect of PALs.
106

107 While the results of the pilot study support reducing the lower limit of accommodative response
108 to 2.15 D, it was decided to reduce the limit further to 2.00 D for two reasons. The first reason
109 relates to the future ability of clinicians in the community to implement the definition of high
110 accommodative lag, as clinicians normally measure accommodative response using monocular
111 estimation method (MEM) retinoscopy or Nott retinoscopy, the former of which measures
112 accommodative lag in quarter-diopter steps. Second, adopting a threshold of 2.00 D helps to
113 ensure that COMET2 will enroll children who truly have higher accommodative lags.
114

115 Impact of Change

116 Recruitment

117 Because sample size for the primary analysis was based on enrolling 100 patients, the study now
118 plans to recruit 100 patients whose accommodative response is in the range required under the
119 new threshold, up to a maximum of 150 patients total.

120

121 Informed Consent

122 No changes will be needed to the informed consent or assent documents.

123

124 Existing Randomized Patients Not Meeting Revised Criterion

125 Approximately 25% of the patients randomized thus far have accommodative response which
126 exceeds the revised criteria. The proposal is that such patients continue in the study, masked,
127 and in their assigned treatment groups. There is no reason to think that patients with less
128 accommodative lag wouldn't benefit from treatment, even though they might not be expected to
129 have the same degree of treatment benefit as would patients with higher amounts of lag. Also,
130 there are no unique safety concerns related to patients with lesser amounts of accommodative lag
131 wearing PALs, in fact, some clinicians prescribe PALs to similar patients in their routine
132 practices based solely on the presence of esophoria.

133

134 Although these patients will be able to continue in the study, given that they were consented into

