397 3. Accommodative response at near (33 cm) is less than 2.00D by non-cycloplegic autorefraction

- 398 4. No strabismus present by cover-uncover test at far, near, and/or near with +2.00D over best
399 subjective refraction
- 400 5. Near esophoria (≥ 2.0 PD) present by alternate prism and cover test (APCT) at near using
401 best refractive correction determined from non-cycloplegic subjective refraction
- 402 6. No current or prior use of PALs, bifocals, or contact lenses in either eye (prior or current use
403 of SVLs is allowed)
- 404 7. No history of any of the following:
- 405 • Strabismus
 - 406 • Amblyopia
 - 407 • Nystagmus
 - 408 • Ocular, systemic, or neuro-developmental condition that might influence refractive
409 development
 - 410 • Ocular surgery which might influence refractive development
 - 411 • Ocular or systemic medications known to affect accommodative response, such as
412 atropine, pirenzepine, and anti-epileptic medications
 - 413 • Diabetes or seizures
- 414 8. Birth weight at least 4.5lbs
- 415

416 **2.2.3 Cycloplegic Autorefraction**

417 If the patient is eligible for screening with cycloplegic autorefraction, this procedure will be
418 performed on both eyes using the Grand Seiko autorefractor after cycloplegia with 2 drops of 1%
419 tropicamide.

- 420 • The protocol for this procedure is described in the Testing Procedures Manual.
- 421

422 Patients are considered eligible for the randomized trial if the refractive error obtained by
423 cycloplegic autorefraction meets all of the following:

- 424 • Spherical equivalent: -0.75 to -2.50 D in each eye
 - 425 • Astigmatism ≤ 1.5 D in each eye
 - 426 • Anisometropia ≤ 1.00 D difference between eyes in spherical equivalent
- 427

428 **2.3 Randomization**

429 Each patient enrolling in the randomized trial will be randomly assigned to one of two treatment
430 groups:

- 431 • Progressive addition lenses (PAL) with a +2.00D addition
 - 432 • Single vision lenses (SVL)
- 433

434 The JAEB Center will construct a master randomization list using a permuted block design
435 stratified by site and by whether the patient has previously worn spectacles, which will specify
436 the order of treatment group assignments.

437

438 The patient's treatment group assignment can be obtained either by completing randomization on
439 the PEDIG website or by contacting the Jaeb Center if internet access is down.

440

441 **2.4 Prescribing Spectacles**

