3.2 Protocol Visits

3.2.1 Examination Procedures

Prior to the patient's examination by the investigator, the clinic coordinator will update the child's history, and will verify the spectacle prescription using a lensometer.

The following procedures will be performed without cycloplegia and by the same methods as were used at the enrollment visit:

1. Subjective refraction of both eyes

- The purpose of the subjective refraction is to determine whether the patient's spectacle prescription should be changed (see section 3.4.1).
 - If the investigator is changing the spectacle correction, the subsequent testing at this visit will be performed with the patient wearing the correction to be prescribed.

2. Oculomotor assessment using cover-uncover test and Alternate Prism and Cover Test (APCT) (see section 2.4.1)

- Both assessments should be performed as follows, without cycloplegia, using the specified correction in trial frames:
 - At distance and near, using the specified correction*
 - At near with +2.00D over the specified correction*

3. Measurement of accommodative response in the right eye by using Grand Seiko open field autorefractor

- Measurement will be taken with patient wearing trial frames with the specified correction* in front of the right eye and an occluder in front of the left eye.

*The specified correction is the patient's current correction unless the spectacle correction is being changed at this visit, in which case it is the new spectacle correction.

The protocols for the above examination procedures are described in the Testing Procedures Manual.

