4.4 Risks of Treatment

Any type of spectacle wear has a minimal risk for injuries related to frames/lens breakage. Single-vision lenses are routinely prescribed for nearsighted children and pose no additional known risks. The risks of wearing progressive addition glasses are largely unknown. Some children may have some difficulty in the first week with reading, going down steps, and seeing things off to the side. It is not known whether wearing this type of glasses for a long period of time has an effect on accommodative response.

The risks of wearing either type of spectacles are the same as those that would be present wearing the given type of spectacles outside of the study.

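### Change in accommodative response is compared by an unadjusted t-test with intervals named only per arm; a baseline-adjusted between-arm difference with its interval would be more precise and harder to misread

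*Protocol*

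**What the plan says.** Protocol section 6.2.1.2 sets out the analysis in one sentence: "Point estimates and 95% confidence intervals for change in accommodative response will be" "calculated at 1 year, 2 years, and 3 years for each treatment group and change in" "accommodative response will be compared between treatment groups using t-tests". Intervals are named for each arm's change. For the comparison of the arms only a t-test is named, with no covariate.

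The same variable decides entry. Section 2.2.2 requires: "Accommodative response at near (33 cm) is less than 2.00D by non-cycloplegic autorefraction". Before Amendment #2 the limit was looser: "response at 33 cm (3.0 D) is less than 2.50 D (i.e., lag of accommodation 0.50 D or greater) as" measured on the same autorefractor. Children who entered under it stay in the trial, and the amendment gives one figure on their distribution: "Approximately 25% of the patients randomized thus far have accommodative response which" lies above the new limit.

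Section 2.2.1 describes a single screening test with this autorefractor, and the protocol describes no later baseline reading. On follow-up, section 3.2.1 says: "The following procedures will be performed without cycloplegia and by the same methods as were used at the enrollment visit". Section 4.4 explains why the outcome matters. Of progressive lenses it says: "It is not known whether wearing this type of glasses for a long period of time has an effect" on accommodation.

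**The concern.** There are two separate issues.

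**Precision.** A t-test on change scores leaves the baseline value unused as a covariate. When the correlation between baseline and follow-up is below 1, regression on baseline gives a smaller variance for the same contrast. With about 45 evaluable children per arm, that helps to answer a question the protocol calls open.

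**Interpretation.** If the baseline is the reading that had to be low, some children qualify on a chance low value and will read higher next time whatever lenses they wear. A per-arm interval for change then covers true change plus this shift. A rise in the progressive-lens arm could look reassuring, or could offset a real fall. The shift also depends on which entry limit applied, so it varies with the mix of children entered before and after Amendment #2.

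**Working it through.** The protocol states no figure for this outcome, so there is none to reproduce.

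**Inputs from the protocol.** Entry limits 2.00 D and 2.50 D; about 25% of those entered under 2.50 D lie above 2.00 D (Amendment #2); 50 per arm with 10% loss (section 6.1.1), so 50 x 0.9 = 45 evaluable.

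**Assumptions.** Normal distribution of response before selection, SD s = 0.35-0.50 D, correlation r = 0.5-0.85 between baseline and follow-up, no true change in either arm.

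**Step 1: mean that matches the 25%.** Solve Φ((2.00 - m)/s) / Φ((2.50 - m)/s) = 0.75.
- s = 0.35: m = 1.78; Φ(0.63)/Φ(2.06) = 0.735/0.980 = 0.75.
- s = 0.50: m = 1.73; Φ(0.53)/Φ(1.53) = 0.703/0.937 = 0.75.

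**Step 2: expected spurious rise.** With k = (limit - m)/s and L = φ(k)/Φ(k), the rise is (1 - r) x s x L.
- 2.00 D limit, smallest: 0.15 x 0.35 x 0.445 = 0.02 D. Largest: 0.5 x 0.50 x 0.492 = 0.12 D.
- 2.50 D limit, smallest: 0.15 x 0.35 x 0.049 = 0.003 D. Largest: 0.5 x 0.50 x 0.131 = 0.03 D.

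**Step 3: per-arm half-width.** The variance of the selected baseline is v = s²(1 - kL - L²). The SD of change is √[(1 - r)²v + s²(1 - r²)]. The half-width is 2.015 x SD/√45.
- s = 0.50, r = 0.5, 2.00 D limit: v = 0.124; SD = √(0.031 + 0.1875) = 0.467; half-width 0.14 D, against a rise of 0.12 D.
- s = 0.35, r = 0.85, 2.00 D limit: v = 0.064; SD = √(0.0014 + 0.0340) = 0.188; half-width 0.06 D, against a rise of 0.02 D.
- At the 2.50 D limit the half-widths are 0.06-0.15 D.

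The expected rise is below the half-width throughout this grid. The bias is still not nil. The chance that a per-arm interval excludes zero is about Φ(rise/SE - 2.015). For the first case this is Φ(0.123/0.0696 - 2.015) = Φ(-0.25), about 40%; across the grid at the 2.00 D limit it runs from about 12% to 40%, against a nominal 5%.

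**Step 4: a higher mean.** The earlier trial's median lag of 0.43 D (section 1.2) and the pilot's 0.35 D shift (Amendment #2) give 3.00 - 0.43 - 0.35 = 2.22 D. With SD 0.5 D and correlations 0.5, 0.7 and 0.9, the rise at the 2.00 D limit is 0.27, 0.16 and 0.05 D, and a per-arm interval excludes zero in about 98%, 84% and 37% of trials. That mean does not fit the 25%: it implies 1 - Φ(-0.44)/Φ(0.56) = 1 - 0.330/0.712 = 54% above 2.00 D among those below 2.50 D.

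**Step 5: the between-arm test.** In 10,000 simulated trials per setting (mean 2.22 D, SD 0.3-0.7 D, correlation 0.5-0.9, 45 per arm, no lens effect), the mean difference between arms was about 0.00 D and the t-test's type I error was 4.6-5.2%.

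**Step 6: gain from adjustment.** Regression on baseline leaves s²(1 - r²), so the proportional reduction is (1 - r)²v / [(1 - r)²v + s²(1 - r²)].
- Largest (s = 0.35, r = 0.5, 2.50 D limit, v = 0.110): 0.0275/(0.0275 + 0.0919) = 23%.
- Smallest with the 25% match (s = 0.50, r = 0.85, 2.00 D limit): 0.0028/(0.0028 + 0.0694) = 4%.
- With means of 2.00-2.50 D instead: about 1-11%.

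No gain is credited here to prior spectacle wear.

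**The case against.** The tempting stronger reading is that selection will show up as a lens effect in both arms. The documents do not support it. The sentence that plans the per-arm intervals goes on to plan the between-arm comparison, and the shift is expected to be equal in randomized arms, so it cancels. Nowhere does the protocol say that per-arm change will be attributed to lenses, and section 4.4 is a risk statement that promises no answer from those intervals.

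A second tempting inference is that per-arm intervals would exclude zero in most plausible cases. That needs a mean of about 2.0-2.5 D. With SD 0.35-0.50 D, such means imply that about 41-85% of children entered under the 2.50 D limit exceed 2.00 D, against about 25% reported. The 2.22 D figure rests on another trial's median and a pilot in young adults.

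It is also fair to say that a t-test on change is valid, that an interval for the difference follows directly from it, and that chapter 6 leaves detail to separate documents. So the unnamed interval is not counted as an omission. How the readings are taken is in the Testing Procedures Manual, which is not at hand.

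Two things stand. The protocol does fix an unadjusted test where a more precise one costs nothing, and per-arm change from a selected baseline is not a clean measure of what happens under a lens. Ageing affects it too, as does follow-up testing in the current correction unless that is being changed (section 3.2.1).

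**Conclusion.** This is a minor improvement to a secondary analysis. The planned test is valid and no error rate is at risk. Adjustment would lower the variance of the between-arm estimate by roughly 1-23%.

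The expected spurious per-arm rise is about 0.02-0.12 D at the 2.00 D limit and 0.003-0.03 D at the 2.50 D limit, below half-widths of about 0.06-0.15 D. These figures rest on normality, the 25% figure, an assumed SD and correlation, and 45 children per arm. A higher population mean, a larger SD or a lower correlation would make the rise larger. Enrolment towards the permitted 150 would narrow the intervals, although some of those children would have entered under the looser limit, where the shift is smaller. The size therefore cannot be settled from the protocol; the direction can.

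**What to change.** In section 6.2.1.2, or in the SAP, replace the t-test on change with the between-arm difference in accommodative response at 1, 2 and 3 years and its 95% confidence interval. Estimate it from a regression on treatment, baseline accommodative response and prior spectacle wear, which is a randomization stratum in section 2.3. Keep the per-arm changes as descriptive, say that they include regression to the mean from the entry limit, and draw conclusions about lens type only from the between-arm difference.

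The cost is a change of wording. No new measurement, visit or patient is needed.
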